10. ASSESSMENT OF SAFETY

The Principal Investigator is responsible for ensuring that all staff involved in the study is familiar with the content of this section.

10.1 Safety parameters

10.1.1 Definition of adverse events

An adverse event is the development of an undesirable medical condition (other than progression of the malignancy under evaluation) or the deterioration of a pre-existing medical condition following or during exposure to a pharmaceutical product, whether or not considered causally related to the product. An undesirable medical condition can be symptoms (e.g., nausea, chest pain), signs (e.g., tachycardia, enlarged liver) or the abnormal results of an investigation (e.g., laboratory findings, electrocardiogram). In clinical studies, an AE can include an undesirable medical condition occurring at any time, including run-in or washout periods, even if no study treatment has been administered.

The term AE is used to include both serious and non-serious AEs.

Laboratory abnormalities: Laboratory abnormalities present at the screening visit will be recorded as pre-treatment signs and symptoms. After study treatment administration, all grade 3 and 4 clinical laboratory results that represent an increase in severity from baseline will be reported as AEs. A grade 1 or 2 clinical laboratory abnormality should be reported as an AE only if it is considered clinically significant by the investigator (i.e. it induces clinical signs or symptoms or requires therapy).

10.1.2 Definition of serious adverse events

A serious adverse event is an AE occurring during any study phase (i.e., screening, run-in, treatment, wash-out, follow-up), at any dose of the study drugs that fulfils one or more of the following criteria:

- Results in death
- Is immediately life-threatening
- Requires in-patient hospitalization or prolongation of existing hospitalization >24 hours
- Results in persistent or significant disability or incapacity
- Is a congenital abnormality or birth defect in offspring of the patient
- Is a pregnancy or pregnancy outcome of spontaneous abortion, missed abortion, benign hydatidiform mole, blighted ovum, fetal death, intrauterine death, miscarriage, or stillbirth.
- Is an important medical event that may jeopardize the patient or may require medical intervention to prevent one of the outcomes listed above:

The causality of SAEs (their relationship to all study treatment/procedures) will be assessed by the investigator(s) and communicated to AstraZeneca.

Events **not** considered to be SAEs are hospitalizations for:

- Admissions as per protocol for a planned medical/surgical procedure or to facilitate a procedure.
- Routine health assessment requiring admission for baseline/trending of health status (e.g., routine colonoscopy).
- Medical/surgical admission for purpose other than remedying ill health state and was planned prior to entry into the study. Appropriate documentation is required in these cases.
- Admission encountered for another life circumstance that carries no bearing on health status and requires no medical/surgical intervention (e.g., lack of housing, economic inadequacy, care-giver respite, family circumstances, administrative).
- Admissions for monitoring of treatment-related infusion reactions that do not otherwise meet the criteria for a SAE.

10.1.3 Durvalumab + tremelimumab adverse events of special interest

An adverse event of special interest (AESI) is one of scientific and medical interest specific to understanding of the Investigational Product and may require close monitoring and rapid communication by the Investigator. An AESI may be serious or non-serious. The rapid reporting of AESIs allows ongoing surveillance of these events in order to characterize and understand them in association with the use of this investigational product.

AESIs for durvalumab ±tremelimumab include but are not limited to events with a potential inflammatory or immune-mediated mechanism and which may require more frequent monitoring and/or interventions such as steroids, immunosuppressants and/or hormone replacement therapy. These AESIs are being closely monitored in clinical studies with durvalumab monotherapy and combination therapy. An immune-mediated adverse event (imAE) is defined as an AESI that is associated with drug exposure and is consistent with an immune-mediated mechanism of action and where there is no clear alternate etiology. Serologic, immunologic, and histologic (biopsy) data, as appropriate, should be used to support an imAE diagnosis. Appropriate efforts should be made to rule out neoplastic, infectious, metabolic, toxin, or other etiologic causes of the imAE.

If the Investigator has any questions in regards to an event being an imAE, the Investigator should promptly contact the Study Physician.

AESIs observed with durvalumab ±tremelimumab include:

- Diarrhea / Colitis and intestinal perforation
- Pneumonitis / ILD
- hepatitis / transaminast increases
- Neuropathy / neuromuscular toxicity (e.g. Guillain-Barré, and myasthenia gravis)
- Endocrinopathies (i.e. events of hypophysitis/hypopituitarism adrenal insufficiency, hyper- and hypothyroidism and type I diabetes mellitus)
- Rash / Dermatitis
- Nephritis / Blood creatinine increases
- Pancreatitis / serum lipase and amylase increases
- Myocarditis
- Myositis / Polymyositis
- Other inflammatory responses that are rare / less frequent with a potential immune-mediated aetiology include, but are not limited to, pericarditis, sarcoidosis, uveitis and other events involving the eye, skin, haematological and rheumatological events, vasculitis, non-infectious meningitis and non-infectious encephalitis.

In addition, infusion-related reactions and hypersensitivity/anaphylactic reactions with a different underlying pharmacological etiology are also considered AESIs.

Further information on these risks (e.g. presenting symptoms) can be found in the current version of the durvalumab and tremelimumab Investigator's Brochures. More specific guidelines for their evaluation and treatment are described in detail in the Dosing Modification and Toxicity Management Guidelines (see **Appendix 1**). These guidelines have been prepared by the Investigator in the exercise of his/her clinical judgment in treating these types of toxicities. These guidelines apply to AEs considered causally related to the study drug/study regimen by the reporting investigator.

If new or worsening pulmonary symptoms (e.g. dyspnea) or radiological abnormality suggestive of pneumonitis/interstitial lung disease is observed, toxicity management as described in detail in the Dosing Modification and Toxicity Management Guidelines (see **Appendix 1**) will be applied. The results of the full diagnostic workup (including high-resolution computed tomography (HRCT), blood and sputum culture, hematological parameters etc) will be captured in the eCRF. It is strongly recommended to perform a full diagnostic workup, to exclude

alternative causes such as lymphangitic carcinomatosis, infection, allergy, cardiogenic edema, or pulmonary hemorrhage. In the presence of confirmatory HRCT scans where other causes of respiratory symptoms have been excluded, a diagnosis of pneumonitis (ILD) should be considered and the Dosing Modification and Toxicity Management Guidelines should be followed.

Pneumonitis (ILD) investigation

The following assessments, and additional assessments if required, will be performed to enhance the investigation and diagnosis of potential cases of pneumonitis. The results of the assessment will be collected.

- Physical examination

Signs and symptoms (cough, shortness of breath and pyrexia, etc.) including auscultation for lung field will be assessed.

Saturation of peripheral oxygen (SpO₂)

- Other items

When pneumonitis (ILD) is suspected during study treatment, the following markers should be measured where possible:

- ILD Markers (KL-6, SP-D) and β-D-glucan
- Tumour markers: Particular tumour markers which are related to disease progression.
- Additional Clinical chemistry: CRP, LDH

10.2 Assessment of safety parameters

10.2.1 Assessment of severity

Assessment of severity is one of the responsibilities of the investigator in the evaluation of AEs and SAEs. Severity will be graded according to the NCI CTCAE v5.0.

The determination of severity for all other events not listed in the CTCAE should be made by the investigator based upon medical judgment and the severity categories of Grade 1 to 5 as defined below.

Grade 1 (mild)	An event that is usually transient and may require only minimal treatment or therapeutic intervention. The event does not generally interfere with usual activities of daily living.
Grade 2 (moderate)	An event that is usually alleviated with additional specific therapeutic intervention. The event interferes with usual activities of daily living, causing discomfort but poses no significant or permanent risk of harm to the patient.
Grade 3 (severe)	An event that requires intensive therapeutic intervention. The event interrupts usual activities of daily living, or significantly affects the clinical status of the patient.
Grade 4 (life threatening)	An event, and/or its immediate sequelae, that is associated with

an imminent risk of death or with physical or mental disabilities that affect or limit the ability of the patient to perform activities of daily living (eating, ambulation, toileting, etc).

Grade 5 (fatal) Death (loss of life) as a result of an event.

It is important to distinguish between serious criteria and severity of an AE. Severity is a measure of intensity whereas seriousness is defined by the criteria in Section 10.1.2. A Grade 3 AE need not necessarily be considered an SAE. For example, a Grade 3 headache that persists for several hours may not meet the regulatory definition of an SAE and would be considered a nonserious event, whereas a Grade 2 seizure resulting in a hospital admission would be considered an SAE.

10.3 Recording of adverse events and serious adverse events

Adverse events will be recorded in RedCap database using a recognized medical term or diagnosis that accurately reflects the event. Adverse events will be assessed by the investigator for severity, relationship to the investigational product, possible etiologies, and whether the event meets criteria of an SAE and therefore requires immediate notification to AstraZeneca/MedImmune Patient Safety.

The following variables will be collected for each AE (and SAE as applicable):

- AE (verbatim)
- The date when the AE started and stopped
- The maximum CTCAE grade reported
- Changes in CTCAE grade
- Whether the AE is serious or not
- Investigator causality rating against the IPs (yes or no)
- Action taken with regard to IPs
- Administration of treatment for the AE
- Outcome

In addition, the following variables will be collected for SAEs:

- Date the AE met criteria for SAE
- Date the Investigator became aware of the SAE
- Seriousness criteria fulfilled
- Date of hospitalization
- Date of discharge
- Probable cause of death
- Date of death
- Whether an autopsy was performed
- Causality assessment in relation to study procedure(s)
- Causality assessment in relation to other medication
- Description of the SAE

The grading scales found in the revised NCI CTCAE version 5.0 will be utilized for all events with an assigned CTCAE grading. For those events without assigned CTCAE grades, the recommendation in the CTCAE criteria that converts mild, moderate, and severe events into

CTCAE grades should be used. A copy of the CTCAE version 5.0 can be downloaded from the Cancer Therapy Evaluation Program website (<http://ctep.cancer.gov>).

Events, which are unequivocally due to disease progression, should not be reported as an AE during the study.

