2.2 Secondary Objectives

- To assess the safety of combining DEB-TACE with durvalumab and tremelimumab in patients with intermediate stage HCC.

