6.2 Dosage and administration

6.3 Definition of Unacceptable Toxicity

The combination of tremelimumab and durvalumab has been previously tested in a dose-escalation study performed by AstraZeneca employing dose ranges of 1-10mg/kg q4weeks (tremelimumab) and 10-20mg/kg q2-4weeks (durvalumab). Patients treated in the 20 mg/kg durvalumab + 1 mg/kg tremelimumab group had the fewest AEs, Grade ≥ 3 AEs, SAEs, and treatment discontinuations due to AEs, but still showed strong evidence of clinical activity. This cohort had a lower number of treatment-related Grade ≥ 3 AEs or treatment related SAEs. No dose-limiting toxicities were reported. This is the dose level we will be administering for this study. Also, PK analysis indicated only minor impact of body weight (WT) on PK of both agents so to minimize errors and for ease of use the company have moved to a fixed-dose schedule of 1500 mg Q4W durvalumab (equivalent to 20 mg/kg Q4W) and 75 mg Q4W tremelimumab (equivalent to 1mg/kg Q4W).

Unacceptable toxicities will be evaluated from the time of first administration of durvalumab or tremelimumab until the Week 6 evaluation (prior to the second dose of durvalumab). Patients who do not remain on the study through the completion of this safety run-in period for reasons other than DLT will be replaced with another patient (see **Section 11.2.4** for details of safety run-in). Grading of unacceptable toxicities will follow the guidelines provided in the Common Terminology Criteria for Adverse Events (CTCAE) version 5.0.

An unacceptable toxicity will be defined as any toxicity occurring during the study that meets the criteria below. Toxicity that is clearly and directly related to the primary disease or to another etiology is excluded from this definition. The following will be unacceptable toxicities:

- Any Grade 4 irAE
- Any \geq Grade 3 colitis
- Any Grade 3 or 4 non-infectious pneumonitis irrespective of duration
- Any Grade 2 pneumonitis that does not resolve to \leq Grade 1 within 3 days of the initiation of maximal supportive care
- Any Grade 3 irAE, excluding colitis or pneumonitis, that does not downgrade to Grade 2 within 3 days after onset of the event despite optimal medical management including systemic corticosteroids or does not downgrade to \leq Grade 1 or baseline within 14 days
- Liver transaminase elevation $> 8 \times$ ULN or total bilirubin $> 5 \times$ ULN (other than the 1st week following DEB-TACE)

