- Any Grade ≥ 3 asymptomatic amylase or lipase levels, hold study drug/study regimen, and if complete work up shows no evidence of pancreatitis, study drug/study regimen may be continued or resumed.

- Any grade \geq 2 myocarditis
- Any \geq Grade 3 non-irAE, except for the exclusions listed below

[figure not shown]
The definition excludes the following conditions:

[figure not shown]
- Grade 3 fatigue lasting \leq 7 days
- Grade 3 dermatologic AEs that are considered mild in severity but only considered grade 3 because of $>30\%$ body surface involvement
- Diarrhea, nausea, or vomiting that resolves to $<$ grade 3 within 24 hours of intervention
- Grade 3-4 hyperglycemia
- Grade 3 endocrine disorder (thyroid, pituitary, and/or adrenal insufficiency) that is managed with or without systemic corticosteroid therapy and/or hormone replacement therapy and the patient is asymptomatic
- Grade 3 inflammatory reaction attributed to a local antitumor response (e.g., inflammatory reaction at sites of metastatic disease, lymph nodes, etc)
- Grade 3 infusion-related reaction (first occurrence and in the absence of steroid prophylaxis) that resolves within 6 hours with appropriate clinical management
- Grade 3 or 4 neutropenia that is not associated with fever or systemic infection that improves by at least 1 grade within 3 days. Grade 3 or Grade 4 febrile neutropenia will be an unacceptable toxicity regardless of duration or reversibility
- Grade 3 or 4 lymphopenia
- Grade 3 thrombocytopenia that is not associated with clinically significant bleeding that requires medical intervention, and improves by at least 1 grade within 3 days
- Isolated Grade 3 electrolyte abnormalities that are not associated with clinical signs or symptoms and are reversed with appropriate maximal medical intervention within 3 days. Isolated Grade 3 amylase or lipase abnormalities that are not associated with clinical signs/symptoms or findings on imaging consistent with pancreatitis

Immune-related AEs are defined as AEs of an immune nature (i.e., inflammatory) in the absence of a clear alternative etiology. In the absence of a clinically significant abnormality, repeat laboratory testing will be conducted to confirm significant laboratory findings prior to designation as an unacceptable toxicity.

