10.3.2 Causality collection

The Investigator will assess causal relationship between the IPs and each AE and answer “yes” or “no” to the question “Do you consider that there is a reasonable possibility that the event may have been caused by the investigational product?”

For SAEs causal relationship will also be assessed for other medication and study procedures. Note that for SAEs that could be associated with any study procedure, the causal relationship is implied as “yes.”

A guide to the interpretation of the causality question is found in Appendix 1.

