10.3.3 Relationship to protocol procedures

The Investigator is also required to provide an assessment of the relationship of SAEs to protocol procedures on the SAE report form. This includes both non-treatment-emergent (i.e., SAEs that occur prior to the administration of IP) and treatment-emergent SAEs. A protocol-related SAE may occur as a result of a procedure or intervention required during the study (e.g., blood collection). The following guidelines should be used by Investigators to assess the relationship of SAEs to the protocol:

- Protocol related: The event occurred due to a procedure or intervention that was described in the protocol for which there is no alternative etiology present in the patient’s medical record.

- Not protocol related: The event is related to an etiology other than the procedure or intervention that was described in the protocol. The alternative etiology must be documented in the study patient's medical record.

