11.2 Methods of statistical analyses

11.2.1 Safety analyses

Safety will be summarized by the percentage of patients with AEs, by type and grade according to NCI CTCAE version 5.0 and attribution. The analysis will be based on safety analysis set.

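### Non-serious adverse events have no causality field for DEB-TACE, procedure causality for SAEs has two conflicting tests, and the run-in definition does not say whether DEB-TACE toxicity counts

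*Combined protocol and SAP*

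**What the plan says.** **Objective and analysis.** Section 2.2 sets the secondary objective: "To assess the safety of combining DEB-TACE with durvalumab and tremelimumab in patients with intermediate stage HCC". Section 11.1.1 includes patients who received DEB-TACE alone in the safety set. Section 11.2.1 summarizes events by type and grade "according to NCI CTCAE version 5.0 and attribution".

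**All adverse events.** The only causality item in the Section 10.3 list is "Investigator causality rating against the IPs (yes or no". Section 10.3.2 frames it as whether there is a reasonable possibility that the investigational product caused the event. Table 8 (Section 15.1) names durvalumab and tremelimumab as those products, and Section 5.3 calls DEB-TACE standard of care. Section 10.3 also tells the investigator to assess possible etiologies, but its list of collected variables has no such item.

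**Serious adverse events.** Section 10.3.2 adds: "For SAEs causal relationship will also be assessed for other medication and study procedures". It continues "Note that for SAEs that could be associated with any study procedure, the causal relationship is implied as" *yes*. Section 10.3.3 calls an SAE protocol related only when it is due to a protocol procedure or intervention "for which there is no alternative etiology present" in the medical record.

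**Run-in.** Section 6.3 states: "Toxicity that is clearly and directly related to the primary disease or to another etiology is excluded from this definition". The same section counts liver enzyme and bilirubin elevations above set limits, with the first week after DEB-TACE as the only DEB-TACE exception. It also counts non-immune toxicity of Grade 3 or higher, apart from listed exclusions.

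**The concern.** The regimen under study has three components, and the form asks about two of them. Unless an event is serious, the attribution dimension of the safety table separates drug-related from everything else, so DEB-TACE harm falls into the same cell as cirrhosis, tumor and intercurrent illness. A report on the safety of the combination could then not say from its attribution data how much non-serious toxicity came from embolization.

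The gap is not confined to minor events. Section 10.2.1 says that a Grade 3 event need not be serious, so a Grade 3 event without a seriousness criterion has no DEB-TACE field.

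In the run-in, a single event can decide the outcome, and two careful investigators could score the same event after DEB-TACE differently.

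**Working it through.** The plan states no figure on this point, so most of the check is a comparison of passages.

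**1. What the attribution column can show.**
- *Event caused by DEB-TACE alone, non-serious:* the answer is *no*. The event is listed as unrelated, with no procedure field.
- *Event between the first DEB-TACE (Week 0) and the first infusion (Week 2):* no study drug has been given, so *no* is the only possible answer. The same holds throughout for patients who receive only DEB-TACE, whom Section 11.1.1 keeps in the safety set. (The synopsis requires at least one drug dose as well; the two definitions also need reconciling.)
- *Event plausibly due to drug and DEB-TACE together:* the question asks for a reasonable possibility, not a sole cause, so the answer should be *yes*.

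Exposure: the planned 20 patients × 1 procedure = 20, and 20 × 4 = 80, where four per patient is the estimate in Section 8.1.2.

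**2. The two SAE tests.** Take an SAE that DEB-TACE and the drugs could each have caused. Section 10.3.2 makes procedure causality *yes* because an association is possible. Under Section 10.3.3 the drugs are an alternative etiology, so the event cannot be protocol related. If the drugs are instead read as a protocol intervention, the conflict remains for an SAE plausibly due to DEB-TACE or to underlying cirrhosis. Neither section says whether DEB-TACE, as standard of care, is a study procedure.

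**3. The run-in definition.** The observation window runs from the first drug dose to Week 6. On the nominal schedule it opens two weeks after DEB-TACE, when the first-week liver exception has passed, and closes before the Week 8 repeat. The liver criterion therefore suggests that elevations in the window count, while the general etiology exclusion could remove them if they are put down clearly and directly to DEB-TACE. The text does not say which governs.

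**4. Illustration of size.** Inputs from Section 11.2.4: proceed with at most 1 event in 6 patients; otherwise add 3 and proceed with at most 2 in 9. I allow at most one event per patient. A true rate *p* and a share *s* of events assigned to another etiology are assumptions, as the documents give neither. The counted rate is q = p(1 − s), and

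P(proceed) = P(X₆ ≤ 1) + P(X₆ = 2) × P(X₃ = 0), with X binomial at rate q.

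- q = 1/3: 0.3512 + 0.3292 × 0.2963 = **0.449**
- q = 1/3 × 0.75 = 0.25: 0.5339 + 0.2966 × 0.4219 = **0.659**

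P(proceed) over a range:

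| True rate p | s = 0 | s = 10% | s = 25% | s = 50% |
|---|---|---|---|---|
| 0.1 | 0.957 | 0.968 | 0.980 | 0.993 |
| 0.2 | 0.781 | 0.826 | 0.885 | 0.957 |
| 0.3 | 0.531 | 0.608 | 0.722 | 0.885 |
| 0.4 | 0.300 | 0.386 | 0.531 | 0.781 |
| 0.5 | 0.139 | 0.210 | 0.353 | 0.659 |

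On a single event: 2 of 6 adds three patients and 1 of 6 proceeds; 3 of 9 pauses and 2 of 9 proceeds.

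**The case against.** DEB-TACE is background standard of care here, so rating causality against the investigational drugs is a defensible convention. Start and stop dates are collected, so timing relative to each procedure can be rebuilt afterwards. Section 10.3.2 refers to Appendix 1 for guidance on the causality question, and that appendix is not in the available text. These points stand and temper the concern. They do not fill the gap: timing is not an attribution, and no guidance on the drug question creates a DEB-TACE field.

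A reader might infer more than the documents support:

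- *That DEB-TACE harm goes uncounted.* It does not. Section 10.1.1 defines adverse events regardless of cause, and Section 11.2.1 tabulates them by type and grade. Exclusion is possible only in the run-in count.
- *That harm from the combination is scored as unrelated.* A joint effect meets the reasonable-possibility question and is not clearly and directly due to something else. Misclassification is possible, but the text does not produce it.
- *That the run-in drops liver toxicity after DEB-TACE.* The exclusion carries a strong qualifier, the liver criterion exempts only the first week, and non-immune Grade 3 or higher events count. The supported statement is that the passages are unreconciled.
- *That "Grade 3 inflammatory reaction attributed to a local antitumor response" is a second route for losing DEB-TACE events.* Its examples are metastatic sites and lymph nodes, and it does not mention DEB-TACE.

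**Conclusion.** The point holds in three parts. First, no causality variable links a non-serious event to DEB-TACE, across some 20 to 80 procedures, so the attribution table serves the combination-safety objective only in part. Second, Sections 10.3.2 and 10.3.3 give conflicting tests of procedure causality for SAEs. Third, Section 6.3 does not say whether DEB-TACE is another etiology, and its liver criterion points a different way from its general exclusion.

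The first two rest on the text alone. For the third, the ambiguity is textual, but its size is not known. The rise from 0.449 to 0.659 depends on an assumed 33.3% rate and an assumed quarter of events excluded; it shows how sensitive the rule is, not that misclassification occurs. The response endpoint is unaffected. This is a worthwhile, inexpensive correction to the safety reporting.

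**What to change.** - **Sections 10.3 and 10.3.2:** for every adverse event, record the relationship to (a) durvalumab/tremelimumab, (b) DEB-TACE, (c) biopsy and (d) disease, with more than one allowed.
- **Section 11.2.1:** keep the drug-related column and add beside it a column for events related to any part of the regimen.
- **Sections 10.3.2 and 10.3.3:** use one test of procedure causality, and state whether DEB-TACE is a study procedure.
- **Section 6.3:** reconcile the etiology exclusion with the liver criterion. The choice is the sponsor's, because Section 4.3 also makes unacceptable toxicity a ground for permanent discontinuation. Whichever reading is adopted, report the run-in count with and without DEB-TACE-attributed events.

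The cost is one form field, wording in four places, and back-fill from source notes for patients already treated, marked as retrospective. The related-event rate may look slightly higher. Even if the run-in is complete, the change improves the final safety report.
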